### **8. DOSING DELAYS/DOSE MODIFICATIONS**

#### **8.1 Phase 1 Dose Modification**

All patients may have dose modifications at any time. During Cycle 1 in the phase 1 portion, however, the DLT must be recorded for safety purposes prior to dose reduction. Patients may have drug held for any reason for up to 14 days before discontinuing study treatment. Refer to Tables 4 - 7 below for specific dose modification instructions.

Patients will undergo therapeutic monitoring with trough levels of Sirolimus on day 2 of cycle 1 before receiving daily dose of Sirolimus on day 2 (+2 day window), day 8, day 15, and day 22 of Cycle 1, on day 1 of each subsequent cycle, unless clinically indicated, and during the End-of-Study visit. Trough levels may be measured at other time points as clinically indicated. As levels  $>18.0\mu\text{g}/\text{L}$  are more likely to be associated with an adverse events, dosing of Sirolimus will be held and/or reduced in the case of trough levels  $>18.0\mu\text{g}/\text{L}$  as indicated in the dose modification table (Table 4). Deviation of this dose modification can be done at the discretion of the treating investigator in discussion with the study principal investigator.

| Sirolimus Monitoring and Dose Modification |   |
|---|---|
| Trough level $> 18\mu\text{g/L}$                  | 
First Event
 
Hold Sirolimus for three days and re-measure trough level on fourth day (+2 day window):
 
 
• If <math>\le 18\mu\text{g/L}</math>, reinstitute drug at original dose
 
• If <math>> 18\mu\text{g/L}</math> hold drug for additional three days and re-measure trough level on fourth day (+2 day window). Repeat dose interruption for additional three days and re-measure trough level the following day until trough level <math>\le 18\mu\text{g/L}</math>, at which time re-institute Sirolimus at next lower dose. Dose reduction constitutes a DLT.
 
 
Second Event
 
Hold Sirolimus for three days and re-measure trough level on fourth day (+2 day window):
 
 
• If <math>\le 18\mu\text{g/L}</math>, reinstitute Sirolimus at next lower dose. Dose reduction constitutes a DLT.
 
• If <math>> 18\mu\text{g/L}</math> hold Sirolimus for additional three days and re-measure trough level on fourth day (+2 day window). Repeat dose interruption for additional three days and re-measure trough level the following day until trough level <math>\le 18\mu\text{g/L}</math>, at which time re-institute Sirolimus at next lower dose. Dose reduction constitutes a DLT.
 
 |

**Table 4.** Sirolimus level dose modification recommendations

8.1.1 Dose Modification for Hepatotoxicity, Nausea/Emesis, and Hyperglycemia

8.1.1.1 **Hepatotoxicity** – Turalio® and Sirolimus should be discontinued if hepatotoxicity is observed as detailed in Table 5.

Reductions or interruptions of the Turalio® dose for toxicity may take place at any time during the study according to the guidelines in [Tables 5 and 6](#). Dose reduction/interruption guidelines for hematologic and nonhematologic treatment-related TEAEs are based on severity. Dose interruptions can be implemented at the discretion of the treating Investigator to manage intolerable or clinically significant toxicity. If a dose interruption is required, study assessments should be performed as scheduled, irrespective of the study drug delay, with the exception of PK assessments, which should be deferred until treatment is resumed. Interruptions due to toxicity lasting  $>14$  d require treatment discontinuation unless the medical monitor approves continuation.

**Columbia University Medical Center**  
**Herbert Irving Comprehensive Cancer Center**  
**Version Date: 04/21/2021**

**Table 6: Additional Liver Evaluation**

| Evaluation  | Comments  |
|--|--|
| Increase frequency of testing liver chemistries to twice per wk, including INR, PT, total and indirect bilirubin, and albumin and continue until liver chemistries have stabilized, and then reduce to weekly until liver chemistries return to normal or baseline.  | Turalio® may be started after liver function tests recover to Grade 0 to 1 or baseline level, and in consultation with the Principal Investigator. |
| Detailed history focusing on medications in a weekly clinic visit and substances used: alcohol, change in medication dosages, new medications added, attention to use of acetaminophen, OTC medication use, and recreational drug use. Check for change in diet or use of dietary supplements, with particular attention to dose and duration of any herbal product. | Suspect medications will be discontinued or substituted for if possible.   |
| Detailed medical history and physical examination seeking new abnormalities in a weekly clinic visits. Frequency of visits as detailed in Table 5.   | Evaluate abnormalities found.  |
| Full serological evaluation for hepatitis A, B, C, and E (IgG and IgM). Check for autoimmune hepatitis with serological laboratory studies.  | If viral hepatitis or autoimmune hepatitis suggested, have patient evaluated by hepatologist.  |
| Liver ultrasound performed to evaluate liver and biliary tree.   | Evaluate any abnormalities found.  |
| Check history for exposure to chemical agents.   | Remove chemical exposure and have patient seen by hepatologist.  |
| Obtain hepatology consult if liver function continues to rise beyond 14 d.   | )Daiichi Sankyo Safety Lead, [name] at [contact]   |
| We request that cases be discussed with the Principal Investigator as defined in the protocol whenever investigational product is being held for liver function test abnormality.   |  |

Ig = Immunoglobulin; INR = international normalized ratio; OTC = over-the-counter.

For suspected cases of cholestatic liver injury (eg, aminotransferase increase concurrent with hyperbilirubinemia, or liver biopsy suggesting cholestasis and/or ductopenia), patients will be followed to assess long-term outcome. Additional diagnostic and follow-up procedures might be implemented as appropriate to fully assess the event.

8.1.1.2 **Nausea and Vomiting** – Turalio® may be associated with nausea and/or emesis that can arise early in the course of therapy. Sirolimus may also contribute to nausea and emesis and may be held as well at the discretion of the treating physician.

| Nausea and Vomiting |   |
|----------------------------|---|
| Grade 3                    | Hold Turalio® dosing until improved to grade 1 or baseline. If delay <48 hours from start of maximal supportive treatment, then restart at cohort with next lower dose for Turalio®.

If delay for ≥48 hours despite maximal supportive treatment, discontinue study treatment. |
| Grade 4                    | If any grade 4 toxicity despite maximal supportive treatment, discontinue study treatment.  |

**Table 7.** Nausea and emesis dose modification recommendations

8.1.1.3 **Hyperglycemia** – immunosuppressive agents, including Sirolimus have been associated with hyperglycemia that responds to treatment.

| Hyperglycemia – Assessed by Fasting Blood Glucose and NOT CTCAE grades  |   |
|--|---|
| Grade 1 = 140-199 mg/dL  | Maintain Turalio® and Sirolimus dosing and institute diet modifications. Address any underlying contributing factors (infection, steroids) and consider initiating blood glucose lowering therapy.  |
| Grade 2 = 200-249 mg/dL  | Maintain Turalio® and Sirolimus dosing and initiate blood glucose lowering therapy.   |
| Grade 3 = 250-399 mg/dL  | Hold only Sirolimus dosing until improved to ≤ Grade 1. 
 
• If ≤7 days, dose reduction is at discretion of treating physician.
 
• If >7 days, dose reduce to cohort with next lower dose of Sirolimus.
 
 |
| Grade 4 = 400 mg/dL or higher

OR

Any hyperglycemia leading to diabetic ketoacidosis, hyperosmolar nonketotic | Discontinue from study drug treatment.  |

|   |  |
|---|--|
| coma, or requiring IV insulin infusion. |  |
|---|--|

**Table 8.** Hyperglycemia dose modification recommendations

Toxicities that occur outside the DLT window will be taken into consideration when determining the RP2D. Reduction/interruption of dosing for AEs may take place at any time. Below are guidelines for dosage modification for Turalio®-related toxicities as well as guidelines for their management. Dose reductions should occur in increments of 200 mg/day, depending on the toxicity grade, as noted in Table 9. These parameters are only a guide and are not intended to supersede the clinical judgment of the treating physician. All adjustments should be made in consultation with the principal investigator. Dosing interruptions longer than three weeks for any reason should generally result in discontinuation from the study, unless the patient has demonstrated a clinical benefit from therapy and would like to continue dosing with study drug after discussion between the investigator and the Sponsor.

| Toxicity Grade
(CTCAE v4)  | Turalio® and
Sirolimus dose changes
during current
treatment period   | Dose adjustments for resumption of treatment   |
|---|--|---|
| Hematologic Toxicity   |  |   |
| Any Grade 4, or Grade 3 neutropenia with fever, or thrombocytopenia with bleeding and except for Grade 4 lymphopenia |  |   |
| 1 st Appearance  | Interrupt until ANC recovers to $\geq 1 \times 10^9/L$ ; growth factor support permitted | Dose reduce one dose level. If dose level 1 at time of AE, discontinue both drugs.            |
| 2 nd Appearance  | Interrupt until ANC recovers to $\geq 1 \times 10^9/L$ ; provide growth factor support   | Dose reduce one additional dose level. If dose level 1 at time of AE, discontinue both drugs. |
| 3 rd Appearance  | Interrupt until ANC recovers to $\geq 1 \times 10^9/L$ ; provide growth factor support   | Dose reduce one additional dose level. If dose level 1 at time of AE, discontinue both drugs. |
| 4 th Appearance  | Discontinue Permanently  | N/A   |
|   |  |   |

| Non-Hematologic Related Grade 3 or Grade 4 not related to abnormal liver function (start symptomatic treatment when possible). |   |   |
|---|---|---|
| 1 st Appearance  | Interrupt until recovered (grade 0-1) and provide supportive management | Dose reduce one dose level. If dose level 1 at time of AE, discontinue both drugs.            |
| 2 nd Appearance  | Interrupt until recovered (grade 0-1) and provide supportive management | Dose reduce one additional dose level. If dose level 1 at time of AE, discontinue both drugs. |
| 3 rd Appearance  | Interrupt until recovered (grade 0-1) and provide supportive management | Dose reduce one additional dose level. If dose level 1 at time of AE, discontinue both drugs. |
| 4 th Appearance  | Discontinue Permanently   | N/A   |

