#### **4.2 Dose Limiting Toxicities for Phase I**

All patients who receive at least one dose of both study drugs will be evaluable for toxicity.

In order for a patient to be evaluable for DLT assessments, the patient must either incur a DLT during the DLT evaluation period or have received at least 80% of the planned doses of Sirolimus and Turalio®. Patients who do not fulfill one of these criteria should be considered non-evaluable for DLT assessment purposes, and be replaced.

A DLT is defined as an AE assessed as being possibly, probably, or definitely related to study drug administration that is:

- Not due to the underlying malignancy;
- Has no clear evidence of an alternative etiology; and
- Meets one of the following CTCAE v.4.03 criteria during the first 56 days of Turalio® and Sirolimus administration:
  - Any Grade  $\geq 4$  hematologic toxicity except grade 4 lymphopenia
  - Grade 3 neutropenia with fever
  - Grade 3 thrombocytopenia with clinically significant bleeding
  - Any circumstance that results in dose reduction.
  - Any Grade  $\geq 3$  non-hematologic toxicity except:
    - Nausea, vomiting, and/or diarrhea of Grade 3 severity that resolves within 3 days with optimal prophylaxis and/or treatment.
    - Grade 3 fatigue that resolves to Grade  $\leq 2$  within 2 days.
    - Grade  $\geq 3$  alkaline phosphatase that is related to underlying malignancy (eg, bone metastasis)
    - For hypercholesterolemia, hypertriglyceridemia, and hyperglycemia if unresolved after appropriate treatment with standard of care.

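### Grade 3 nausea or vomiting under 48 hours is a Phase 1 DLT through the Table 7 dose reduction despite the Section 4.2 exemption, while an episode of roughly 48 to 72 hours may meet no DLT criterion

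*Combined protocol and SAP*

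**What the plan says.** Four pieces of the protocol bear on this.

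- **Section 4.2, exemption.** Under the Grade 3 or higher non-hematologic criterion, the first exception is "Nausea, vomiting, and/or diarrhea of Grade 3 severity that resolves within 3 days with optimal prophylaxis and/or treatment". Short Grade 3 fatigue is excepted in the same list.
- **Section 4.2, separate criterion.** At the same level as the non-hematologic criterion, and outside its exceptions, stands "Any circumstance that results in dose reduction". Meeting any one criterion is enough.
- **Section 8.1.1.2, Table 7 (Phase 1).** For Grade 3 nausea or vomiting, Turalio is held until improvement to grade 1 or baseline. Then: "If delay <48 hours from start of maximal supportive treatment, then restart at cohort with next lower dose for Turalio". Otherwise: "If delay for ≥48 hours despite maximal supportive treatment, discontinue study treatment". Section 8.1 gives this table the status of an instruction: "Refer to Tables 4 - 7 below for specific dose modification instructions".
- **Section 8.1, Table 9.** For the first related Grade 3 or 4 non-hematologic event not related to abnormal liver function, the entry is "Dose reduce one dose level. If dose level 1 at time of AE, discontinue both drugs". The paragraph that introduces Table 9 adds "These parameters are only a guide and are not intended to supersede the clinical judgment of the treating physician".

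Table 4 repeats, for sirolimus trough events, that a dose reduction is a DLT. Section 4.2 also makes a patient non-evaluable, to be replaced, if the patient has neither a DLT nor at least 80% of planned doses. No text says whether a reduction made for an exempt event counts as a DLT, or whether a discontinuation for toxicity does.

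**The concern.** An exemption for short episodes is meant to keep manageable events out of the DLT count. Here the management table pulls the shortest ones back in through the dose-reduction criterion, and sends longer ones down a path that may avoid every criterion. A milder course can then score worse than one that ends treatment.

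The DLT indicator is the only outcome the TITE-CRM uses. Section 13.3.1 will report DLT proportions by level and the final model estimates, and Section 9.7 says the method identified dose level 3 as the Phase 2 dose. Section 9.1 lists nausea and vomiting as common with Turalio and nausea as common with sirolimus, so the event type is not remote, although those lists give no Grade 3 rates.

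**Working it through.** **Step 1. Apply the rules by duration.** Take a related Grade 3 nausea or vomiting episode inside the 56-day window, and as a simplification treat delay and duration as equal.

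| Duration | Section 4.2 exemption | Table 7 action | Dose-reduction criterion | Literal result |
|---|---|---|---|---|
| under 48 h | exempt | restart at lower Turalio dose | met | DLT |
| 48 to 72 h | exempt | discontinue | not met, if stopping is not a reduction | no criterion met |
| over 72 h | not exempt | discontinue | not needed | DLT |

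The result is not monotone in duration. The exemption has no effect under 48 hours and takes effect only in the middle band.

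**Step 2. Where the middle band goes.** With no DLT, the patient stays evaluable only with at least 80% of planned doses. If planned doses means the full window, that is 0.80 × 56 = 44.8 days; if it means Cycle 1, 0.80 × 28 = 22.4 days. The protocol does not say which. Section 8.1.1.2 notes that nausea can arise early, so such a patient could fall below either threshold and be replaced. Section 7.5 foresees replacement only for withdrawals other than toxicity or progression, so it does not fit that outcome.

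**Step 3. Reproduce the protocol's example.** Section 4.1 describes a simulated trial (Figure 4) with these final data:

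| Level | 2 | 3 | 4 | 5 |
|---|---|---|---|---|
| Patients | 2 | 3 | 10 | 3 |
| DLTs | 0 | 0 | 1 | 2 |

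Inputs from Section 4.1: empiric model p_k = s_k^exp(b), b ~ N(0, 1.34), target 0.25, indifference interval 18% to 32%, so half-width (0.32 − 0.18)/2 = 0.07. The prior-MTD level is not given. Assuming level 2, the skeleton is 0.124, 0.250, 0.398, 0.542, 0.666. With complete follow-up, the level 4 estimate is 18.6% (90% interval 6% to 37%) and the MTD is level 4, all as the protocol states. Assuming level 1 gives 19.5%. Levels 3, 4 and 5 give 17.7%, 16.8% and 15.9%, with level 5 selected. Level 2 is therefore the best-supported assumption.

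**Step 4. Change the DLT count, keeping dose assignments fixed.** The selected level is the one whose estimate is nearest 0.25.

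| Change | Level 3 | Level 4 | Level 5 | MTD |
|---|---|---|---|---|
| none | 0.080 | 0.186 | 0.327 | 4 |
| minus one at level 4 | 0.040 | 0.118 | 0.242 | 5 |
| minus one at level 5 | 0.049 | 0.134 | 0.263 | 5 |
| plus one at level 2 | 0.158 | 0.293 | 0.443 | 4 |
| plus one at level 3 | 0.137 | 0.267 | 0.416 | 4 |
| plus one at level 4 | 0.124 | 0.249 | 0.397 | 4 |
| plus one at level 5 | 0.115 | 0.238 | 0.385 | 4 |
| plus one at 3, one at 4 | 0.184 | 0.325 | 0.474 | 3 |
| plus two at level 4 | 0.172 | 0.310 | 0.459 | 4 |
| plus one at 3, one at 5 | 0.177 | 0.316 | 0.465 | 4 |
| plus one at 4, one at 5 | 0.164 | 0.300 | 0.450 | 4 |

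The shift to level 3 for one at level 3 and one at level 4 is narrow: 0.25 − 0.184 = 0.066 against 0.325 − 0.25 = 0.075.

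Reclassification can go either way. If short episodes were counted and the reconciled rule exempts them, DLTs are removed. If middle-band episodes were left out and the rule counts them, DLTs are added.

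**The case against.** Several arguments on the other side are sound.

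- **The rule under 48 hours is determinate.** The exemption qualifies one criterion only, and dose reduction is a separate sufficient one. Read literally, the patient is a DLT. This stands: the result is not undefined, but it defeats the exemption for the shortest episodes.
- **The middle band is conditional.** It exists only if permanent discontinuation is not a dose reduction, which the text leaves open. The clocks also differ. Table 7 counts from the start of maximal supportive treatment to grade 1 or baseline; Section 4.2 gives neither a start point nor a target grade. An episode still unresolved 48 hours after maximal support began may already be past 3 days, so the band is approximate and could be narrow.
- **The tables leave room for judgment.** Table 9 is captioned as recommended and introduced as a guide, so a reader who infers that it obliges a reduction for every related Grade 3 or 4 event goes too far. It creates a tension with the diarrhea and fatigue exemptions; it does not necessarily undo them. Table 7's caption also speaks of recommendations, but Section 8.1 calls Tables 4 to 7 instructions, and the guide-only sentence belongs to Table 9. If discretion does extend to Table 7, the DLT status of a short episode turns on the physician's choice to reduce.

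A reader might also infer that DLTs in days 29 to 56 go unrecorded, because Section 8.1 says "During Cycle 1 in the phase 1 portion, however, the DLT must be recorded for safety purposes prior to dose reduction". The documents do not support that. The sentence governs the order of recording and reduction in Cycle 1, while Sections 4.1 and 4.2 set the window at 8 weeks and 56 days without ambiguity.

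**Conclusion.** The inconsistency is in the text and should be corrected. Under the literal rules an episode below 48 hours is a DLT despite the exemption, and one of roughly 48 to 72 hours may meet no criterion and may leave the DLT data through replacement. The second half rests on discontinuation not being a dose reduction and on the two clocks roughly agreeing.

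It would be too strong to say that the exemption never operates: it does so in the middle band. It would also be too strong to say that the Phase 2 dose was affected. The documents give no count of such episodes, and Section 8.1 says that toxicities outside the DLT window also inform the RP2D. The Figure 4 check uses simulated data, an assumed prior-MTD level and fixed dose assignments. It shows that one DLT removed can raise the selected level, that one added does not lower it, and that two added lower it only for some placements. That sensitivity is enough to require one stated rule behind the reported estimates, and no more.

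**What to change.** 1. Reconcile Section 4.2 with Tables 7 and 9. State whether a reduction made for an otherwise exempt event counts as a DLT, and whether discontinuation for toxicity does. Which clinical rule should prevail is for the investigators; the passages need only agree.
2. Give the 3-day exemption and the 48-hour rule a common clock, or define each one's start and end.
3. Align the replacement rules in Sections 4.2 and 7.5 for a patient stopped for toxicity without a DLT.
4. Section 13.1 says the 18 Phase 1 patients are enrolled. Check how any Grade 3 nausea, vomiting, diarrhea or fatigue episodes among them, and among any replaced patients, were classified. If any are affected, report the Section 13.3.1 DLT proportions and TITE-CRM estimates under both readings; if none are, say so.

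The cost is clarifying wording, a review of the DLT classification for 18 patients plus any replaced, and at most one additional model run.

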**Table 9: Recommended Turalio® and Sirolimus Dose Modifications**

Dose interruptions for Grade 2 non-hematologic toxicity for up to 1 week can be implemented at the discretion of the treating physician to manage intolerable or clinically significant toxicity. No dose reduction is required when resuming treatment.

## **8.2 Phase 2 Dose Modification**

Patients may have dose modifications at any time. Patients may have either drug held for any reason for up to 21 days before discontinuing study treatment. Refer to Tables 10 – 14 below for specific dose modification instructions.

### **8.2.1 Dose Modification for Sirolimus**

Patients will undergo therapeutic monitoring with trough levels of Sirolimus on day 2 of cycle 1 before receiving daily dose of Sirolimus on day 2 (+2 day window), day 8, day 15, and day 22 of Cycle 1, on day 1 of each subsequent cycle, unless clinically indicated, and during the End-of-Study visit. Trough levels may be measured at other time points as clinically indicated. As levels >18.0 $\mu$ g/L are more likely to be associated with an adverse event, dosing of Sirolimus will be held and/or reduced in the case of trough levels >18.0 $\mu$ g/L as indicated in the dose modification table (Table 10). Deviation of this dose modification can be done at the discretion of the treating investigator in discussion with the study principal investigator.

| Sirolimus Monitoring and Dose Modification |  |
|---|--|
| Trough level > 18 $\mu$ g/L                       | 
First Event
 
Hold Sirolimus for three days and re-measure trough level on fourth day (+2 day window):
 
 
• If <math>\leq</math> 18<math>\mu</math>g/L, reinstitute drug at 2 mg orally daily.
 
• If <math>></math> 18<math>\mu</math>g/L hold drug for additional three days and re-measure trough level on fourth day (+2 day window). Continue dose hold for up to 21 days total, re-measuring trough levels every fourth day (+2 day window) until trough level <math>\leq</math> 18<math>\mu</math>g/L, at which time re-institute Sirolimus at 1mg orally daily.
 
 
Second Event
 
Hold Sirolimus for three days and re-measure trough level on fourth day (+2 day window):
 
 
• If <math>\leq</math> 18<math>\mu</math>g/L, reinstitute Sirolimus at 1mg orally daily.
 
• If <math>></math> 18<math>\mu</math>g/L hold Sirolimus for additional three days and re-measure trough level on fourth day (+2 day window). Continue dose hold for up to 21 days total, re-measuring trough levels every fourth day (+2 day window) until trough level <math>\leq</math> 18<math>\mu</math>g/L, at which time re-institute Sirolimus at 0.5mg daily.
 
 
For Third Event or higher, hold Sirolimus for three days and re-measure trough level on fourth day (+2 day window). If <math>\leq</math> 18<math>\mu</math>g/L, reinstitute Sirolimus at 0.5mg daily. If Sirolimus trough level is <math>></math> 18<math>\mu</math>g/L at the 0.5mg orally daily dose, the patient should discontinue study treatment.
 |

**Table 10.** Sirolimus level dose modification recommendations

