### 8.2.2 Dose Modification for Hepatotoxicity, Nausea/Emesis, and Hyperglycemia

**Hepatotoxicity** – Turalio® and Sirolimus should be discontinued if hepatotoxicity is observed as detailed in Tables 5 and 6.

Reductions or interruptions of the Turalio® dose for toxicity may take place at any time during the study according to the guidelines in [Tables 5 and 6](#). Dose reduction/interruption guidelines for hematologic and nonhematologic treatment-related TEAEs are based on severity. Dose interruptions can be implemented at the discretion of the treating Investigator to manage intolerable or clinically significant toxicity. Interruptions due to toxicity lasting  $>$  21 d require treatment discontinuation unless the medical monitor approves continuation.

**Nausea and Vomiting** – Turalio® may be associated with nausea and/or emesis that can arise early in the course of therapy. Sirolimus may also contribute to nausea and emesis and may be held as well at the discretion of the treating physician.

| Nausea and Vomiting |   |
|----------------------------|---|
| Grade 3                    | Hold Turalio® and Sirolimus dosing until improved to grade 1 or baseline. If improvement of symptoms in less than 48 hours from start of maximal supportive treatment, then restart at 400mg orally in AM and 400mg orally in PM daily.

If symptoms do not improve within 48 hours despite maximal supportive treatment, hold Turalio® and Sirolimus, and consult with Principal Investigator. |
| Grade 4                    | If grade 4 toxicity despite maximal supportive treatment, hold Turalio® and Sirolimus, and consult with Principal Investigator.   |

**Table 12.** Nausea and emesis dose modification recommendations

**Hyperglycemia** – immunosuppressive agents, including Sirolimus have been associated with hyperglycemia that responds to treatment.

| Hyperglycemia – Assessed by Fasting Blood Glucose              |   |
|---|---|
| Grade 1 = > ULN - 160 mg/dL   | Maintain Turalio® and Sirolimus dosing and institute diet modifications. Address any underlying contributing factors (infection, steroids) and consider initiating blood glucose lowering therapy.  |
| Grade 2 = > 160 - 250 mg/dL   | Maintain Turalio® and Sirolimus dosing and initiate blood glucose lowering therapy.   |

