| Grade 3 = > 250-500 mg/dL

OR

Hospitalization indicated. | Hold only Sirolimus and initiate blood glucose lowering therapy. Reinstitute Sirolimus if $\leq$ Grade 2.

• If $\leq$ 7 days, dose reduction is at discretion of treating physician.

• If $>$ 7 days, dose reduce to 1mg orally daily if study related. |
| Grade 4 = > 500 mg/dL

OR

Life threatening consequences. | Discontinue from study drug treatment if AE considered study related.   |

**Table 13.** Hyperglycemia dose modification recommendations

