### 8.2.3 Dose Modification for Non-Hematologic Toxicity

Reduction/interruption of dosing for other AEs may take place at any time. Below are guidelines for dosage modification for Turalio®-related toxicities as well as guidelines for their management. Dose reductions should depend on the toxicity grade, as noted in Table 14. These parameters are only a guide and are not intended to supersede the clinical judgment of the treating physician. All adjustments should be made in consultation with the principal investigator. **Dosing holds longer than 21 days for any reason should generally result in discontinuation from the study**, unless the patient has demonstrated a clinical benefit from therapy and would like to continue dosing with study drug after discussion between the investigator and the Principal investigator.

| Toxicity Grade (CTCAE v4)   | Turalio® and Sirolimus dose changes during current treatment period                      | Dose adjustments for resumption of treatment  |
|---|--|---|
| Hematologic Toxicity   |  |   |
| Any Grade 4, or Grade 3, neutropenia with fever, or thrombocytopenia with bleeding, except for Grade 4 lymphopenia             |  |   |
| 1 st Appearance  | Interrupt until ANC recovers to $\geq 1 \times 10^9/L$ ; growth factor support permitted | Dose reduce Turalio® to 400mg orally in AM and 400mg orally in PM daily.  |
| 2 nd Appearance  | Interrupt until ANC recovers to $\geq 1 \times 10^9/L$ ; provide growth factor support   | If Turalio® total daily dose at 800mg orally, dose reduce Turalio® to 200mg in AM and 400mg in PM. If Sirolimus 2.0mg, decreased to 1.0mg.  |
| 3 rd Appearance  | Interrupt until ANC recovers to $\geq 1 \times 10^9/L$ ; provide growth factor support   | Discontinue study treatments unless subject deriving clinical benefit. Consult with Principal investigator and consider decreasing Turalio® to 200mg twice daily and decrease Sirolimus to half the dose unless at 0.5mg. |
| 4 th Appearance  | Discontinue Permanently  | N/A   |
| Non-Hematologic Related Grade 3 or Grade 4 not related to abnormal liver function (start symptomatic treatment when possible). |  |   |
| 1 st Appearance  | Interrupt until recovered (grade 0-1) and provide supportive management.                 | Dose reduce Turalio® to 400mg orally in AM and 400mg orally in PM daily and Sirolimus to 1.0mg orally in AM.  |

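### Two Phase 2 restart rules in Section 8.2 name a fixed dose whatever dose was held: Table 10 can double sirolimus already cut to 1 mg, and Table 12 can raise Turalio from 600 to 800 mg/day

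*Combined protocol and SAP*

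**What the plan says.** Phase 2 patients start at Turalio 1000 mg/day (400 mg morning, 600 mg evening) with sirolimus 2 mg (Section 9.6.1). Section 8.2 refers sites to its tables for dose modification.

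- **Table 10 (Section 8.2.1).** The lead-in gives the reason for acting: levels above 18.0 µg/L "are more likely to be associated with an adverse event, dosing of Sirolimus will be held and/or reduced" as the table directs. At a first event, sirolimus is held for three days. If the trough is then at or below 18 µg/L, the instruction is "reinstitute drug at 2 mg orally daily".
- **Table 12 (Section 8.2.2).** For Grade 3 nausea or vomiting, dosing is held. If symptoms improve in under 48 hours, "then restart at 400mg orally in AM and 400mg orally in PM daily", which is 800 mg/day.

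Three other rules can lower sirolimus to 1 mg before any trough event:

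- Table 13, Grade 3 hyperglycemia lasting more than 7 days: "dose reduce to 1mg orally daily if study related".
- Table 14, first non-hematologic appearance: "Dose reduce Turalio® to 400mg orally in AM and 400mg orally in PM daily and Sirolimus to 1.0mg orally in AM".
- Table 14, second hematologic appearance, in a patient at 800 mg/day: "dose reduce Turalio® to 200mg in AM and 400mg in PM. If Sirolimus 2.0mg, decreased to 1.0mg". This row also takes Turalio to 600 mg/day.

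**The concern.** Both restart rules assume that the patient is still on the starting regimen, or at least not below the printed figure. Nothing in either rule limits it to such patients.

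A patient on sirolimus 1 mg with a first high trough has just shown that 1 mg gave too much exposure, and the printed response is 2 mg. A patient whose Turalio was cut to 600 mg/day for repeated hematologic toxicity, and who then has Grade 3 vomiting, would restart on a higher dose than the one that was stopped.

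Safety at the recommended Phase 2 dose is a Phase 2 primary objective (Section 1.1). Dose increases triggered by toxicity or by high drug levels would harm patients and blur that assessment. The PFS sample size is not affected.

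**Working it through.** The plan gives no figure to reproduce here. The check is to trace each rule from each dose the plan itself can produce. Doses are written as Turalio mg/day / sirolimus mg, starting at 1000/2.

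**Sirolimus, Table 10, first event cleared at the first re-check**

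| Earlier event | Rule | Dose reached | Sirolimus named at restart | Ratio |
|---|---|---|---|---|
| None | – | 1000/2 | 2 mg | 2/2 = 1.0 |
| Related Grade 3 hyperglycemia over 7 days | Table 13 | 1000/1 | 2 mg | 2/1 = 2.0 |
| First non-hematologic event | Table 14 | 800/1 | 2 mg | 2/1 = 2.0 |
| Two hematologic events | Table 14 | 800/2, then 600/1 | 2 mg | 2/1 = 2.0 |

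The rule fits the first line and doubles the dose on the other three. None of these routes depends on whether Table 14 appearances are counted per heading or overall.

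*Possible effect on exposure (assumption).* If troughs are proportional to dose and the cause persists, a trough above 18 µg/L at 1 mg becomes one above 18 × 2 = 36 µg/L at 2 mg. If the cause was temporary the effect is smaller, and the trough may stay at or below 18 µg/L.

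*Time to the next scheduled check.* After Cycle 1, scheduled troughs fall on day 1 of each 28-day cycle. If a high day 1 trough is acted on at once, the re-check falls on day 4 to 6. The next scheduled trough is on day 29, which is 29 − 6 = 23 to 29 − 4 = 25 days later. Earlier checks are allowed if clinically indicated.

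**Turalio, Table 12, Grade 3 improving within 48 hours**

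- From 1000: restart at 800, a cut of 200 mg/day.
- From 800: restart at 800, no change.
- From 600 (after two hematologic events): restart at 800, a rise of 200 mg/day; 800/600 = 1.33.

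*How uncommon the last path is (illustration on assumptions).* Take the first three events to be hematologic, hematologic, vomiting, in that order. Assume that p = 10% to 25% of patients have an event per 8 weeks, at a constant rate not lowered by dose cuts, and that the three kinds (hematologic, vomiting, other non-hematologic) are equally likely. Assume a median of 6 to 18 weeks on treatment, borrowing the plan's two PFS medians. With a = −ln(1 − p)/8, b = ln 2/median and r = a/(a + b), the expected number among 25 patients is 25 × r³/27.

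- High corner (p = 25%, 18 weeks): r = 0.483, r³ = 0.113, 25 × 0.113/27 = 0.10 patients.
- Low corner (p = 10%, 6 weeks): r = 0.102, r³ = 0.0011, 25 × 0.0011/27 = 0.001 patients.

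**Comparison with Phase 1.** For a first cleared trough, Table 4 (Section 8.1) returns the patient to the original dose. For Grade 3 vomiting, Table 7 (Section 8.1.1.2) steps to the cohort with the next lower Turalio dose. Both are relative to the patient's own dose. The Phase 2 tables replaced them with figures that suit the starting regimen.

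**The case against.** The strongest reply is that nobody would read Table 10 as ordering an increase. The lead-in speaks of holding or reducing, the verb in the rule implies going back to something, and 2 mg is simply the Phase 2 starting dose. Section 8.2.1 also lets the treating investigator depart from Table 10 in discussion with the study principal investigator. Section 8.2.3 calls its parameters a guide and requires consultation.

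Much of this stands. The intent was very probably a return to the patient's own dose, and consultation should catch many cases. But the lead-in refers the reader to the table for what to do, and the table prints a number. The discretion clauses permit a departure without saying what the right dose is. In Table 12, the consultation step is printed for the slower-improving and Grade 4 branches, not for restart within 48 hours.

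The second reply is that the sirolimus case is narrow. It needs a first trough above 18 µg/L at 1 mg when none was recorded at 2 mg, so something must have changed. That is fair, and the documents give no rate for it. The plan does provide for high troughs at a reduced dose, since it states what to do when one occurs "at the 0.5mg orally daily dose, the patient should discontinue study treatment". That sentence follows the third-event rule, however, so it is only modest support for a first event at 1 mg.

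**Conclusion.** The point holds for two rules. Table 10's first-event restart doubles sirolimus (1 to 2 mg) on three routes that the plan itself creates, contrary to its own lead-in. Table 12's restart within 48 hours can raise Turalio from 600 to 800 mg/day, on an uncommon path. How many patients would be affected is unknown. The 36 µg/L figure and the 0.001 to 0.1 patient range rest on the assumptions stated with them. Tables 5 and 11 are not in the supplied text and were not judged.

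A reader might infer more, and the documents do not support it:

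- **That all of Section 8.2 fits only a patient at 1000/2, or that Table 14 never cuts Turalio at 800 mg/day.** Its second hematologic row cuts 800 to 600 mg/day. Its second non-hematologic row deliberately keeps 800 mg/day and cuts sirolimus to 0.5 mg instead.
- **That Table 14's first hematologic row, "Dose reduce Turalio® to 400mg orally in AM and 400mg orally in PM daily", wrongly leaves a patient at 800 mg/day.** That depends on how appearances are counted, which the table does not say.
- **That repeat vomiting at 800 mg/day must lead to 600 mg/day.** Keeping 800 mg/day is a dosing trade-off that the documents do not settle.
- **That sirolimus could go from 0.5 to 2 mg.** Table 10's own stopping sentence ends treatment for a high trough at 0.5 mg.

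**What to change.** Amend Section 8.2 in three places:

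1. Add a general rule: *No drug restarts above the dose held.*
2. Table 10, first event with the trough back at or below 18 µg/L: replace the fixed 2 mg with *the dose held*. The stopping rule at 0.5 mg stays.
3. Table 12, Grade 3 improving within 48 hours: restart Turalio at *800 mg/day or the dose held, whichever is lower*.

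A patient still at 1000/2 is treated exactly as now. The cost is a wording amendment and a memo to sites, with no new patients, visits or tests. The downside is slightly lower exposure in a few patients: sirolimus 1 mg instead of 2 mg, or Turalio 600 instead of 800 mg/day. These are patients who have just had a high trough or a Grade 3 event on the lower dose.
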